This protocol also addresses the need for pilot data to provide the empirical basis for future within-subject cross-over studies. The pilot data will inform the need to account for practice effects while estimating magnitude and duration of treatment effects from a single session of iTBS alone and a single session of iTBS + APT. As iTBS can now be tailored to each Veteran's unique neuropathology and because a single iTBS session can create a potentiated neural environment, iTBS is ideal to study alone. For healthy controls, one session of iTBS to the dorsal-lateral-prefrontal cortex (DLPFC), for example, induces gains in executive functioning. These immediate effects enhance feasibility of future cross-over studies explicating the constellation of Veteran-specific factors related to a Veteran's responses to multiple interventions. APT is ideal for pairing with iTBS, in part, because APT can be tailored to each Veteran's unique global and domain specific cognitive challenges. The tenets of metaplasticity also suggest that APT is ideal because APT is based on principles of exercise-dependent plasticity where novel training-exercises across five domains are provided to deliver stimuli of differing intensity. When APT is provided after iTBS, the provision of targeted APT stimuli during the time of iTBS enhanced plasticity is thought to regulate the plasticity ultimately optimizing cognitive gains as well as carry over of training-related gains.

Testing the scalability of an approach to feasibly and effectively tailor iTBS and APT for Veterans across stroke and TBI, advances rehabilitation research by enabling future research addressing the need for an empirical basis to tailor a broad range of cognitive rehabilitation strategies for Veterans across neurologic diagnoses. If the scientific basis for determining how-to feasibly and effectively tailor cognitive restoration interventions remain undeveloped, then Veterans with persisting cognitive impairments will continue to have diminished quality of life and sub-optimal function, ultimately relying on caregivers for performing daily activities.

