### 3.0 Objectives

**Aim 1: Elucidate merits of transdiagnostic sampling.** Within the two intervention groups (Group 1: n = 24, Active iTBS and Active iTBS + APT; Group 2: n = 24, Placebo iTBS and Placebo iTBS + APT), we expect that (1i) neurologic diagnosis (stroke, TBI) will not moderate the effect of Active iTBS or Active iTBS + APT on Maximum Cognitive Gain as assessed by the Modified Digit Span (MDS) and the Streamlined AMPS (AMPS).

**Aim 2: Obtain pilot data to inform estimation of treatment and practice effects.** We will gather pilot data regarding the magnitude and duration of treatment effects as well as MDS and AMPS practice effects. As we anticipate (2i) greater immediate gains in IADL performance (AMPS) after Active iTBS + APT when compared to Active iTBS alone, we will compare Maximum Cognitive Gains (MCG) on MDS with MCG on AMPS between the Active iTBS and Active iTBS + APT groups to determine if MCGs differ in magnitude. We will also determine if

Active iTBS + APT trend lines indicate an additive treatment effect of APT on MDS and/or AMPS. We also anticipate (2ii) some persisting treatment effects and to explicate these effects we will examine effects for Active iTBS and Active iTBS + APT in the short-term (post-pre-treatment), long-term (2 weeks after a session) and cumulatively across treatment sessions. Since the AMPS uses a unique task during each testing interval and MDS uses 1 of 6 alternate test forms, we will determine (2iii) presence and magnitude of practice effects by testing whether prior exposure to MDS or AMPS results in MDS or AMPS gains for Placebo iTBS.

**Aim 3: Explicate study attrition by perceived suitability of aspects the study design and the relationship between this perceived suitability and fatigue as well as mood.** We will test the ideas that (3i) Attrition rates do not differ by stroke and TBI groups, (3ii) Veterans across stroke and TBI have similar perceptions regarding suitability of the number and type of tests as well as number of study-days, and (3iii) perceived suitability is related to Veteran-reported fatigue and mood.

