**Figure 1. Four Step Screening Process: Summary of Exclusion Criteria by Steps**

For this within-subject placebo-controlled partially-blinded treatment protocol (Fig 2), we will enroll 48 medically stable Veterans with stabilized recovery trajectories after a stroke or a TBI and who have a homogeneous level of moderately impaired cognitive function persisting after standard rehabilitation.

An equal number of Veterans with stroke/TBI (24-stroke; 24-TBI) will be enrolled, but we will over-sample females (Figure 2). For each iTBS group to include an equal number of Veterans with stroke/TBI, Veterans will be randomly assigned by diagnostic groups, to receive Active iTBS or Placebo iTBS. To measure immediate effects (ImE), an equal number of Veterans with stroke/TBI within each iTBS group will be randomly assigned to be tested with the Modified Digit Span (MDS) or AMPS, three times at 30 min intervals. Persisting effects (PE) tests will be administered to all participants at five timepoints including prior to and after Active iTBS or Placebo iTBS and 2-weeks later prior to the 2nd intervention, where all Veterans receive APT paired with their assigned iTBS (Active iTBS + APT or Placebo iTBS + APT). The alternate ImE test is then administered three times at 30 min intervals, followed by re-administration of all PE tests. Two weeks later, all PE tests are administered a 5th time (B4). ImE and PE measures are used to define magnitude and duration of cognitive change. Randomization (SAS Proc Plan) will be managed by one un-blinded researcher who will not provide interventions or conduct testing.

**Figure 2. Study Design (ImE = Immediate Effects Tests; AMPS = AMPS or MDS = Modified Digit Span; PE = Persisting Effects Tests for all participants; Study Day-1: Obtain Covariates and Treatment preparation information; B0 = Pre-Study-Day-2; B1 = Post-Study-Day-2; After 2-Weeks B2 = Pre-Study-Day-3; B3 = Post-Study-Day-3; After 2-Weeks B4 = Study-Day 4)**

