**Study-Day 2 (4 days after Study Day 1)(~8 hours):**

- 1. PE testing battery
- 2. A single session of **Active** iTBS or **Placebo** iTBS
- 3. Randomly assigned ImE test (MDS or AMPS), administered 3-times at 30 min intervals, each interval includes 5 to 15 min of rest).
- 4. PE testing battery
- 5. Suitability ratings 1-3

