Average Placebo iTBS + APT MCG using t-tests for continuous data and z-tests for binary data. Using MLM, we will also determine if Active iTBS is related to more MDS or more AMPS gains. The group (Active iTBS or Placebo iTBS) by time interaction parameter will be used to examine if Active iTBS has a differential trend compared to Placebo iTBS. For 2i, we will also use MLM to identify presence of an additive effect of APT by examining Active iTBS + APT trend lines. For both the AMPS and the MDS outcomes, the group (Active iTBS + APT or Placebo iTBS + APT) by time interaction parameter will be used to examine if the Active iTBS + APT has a differential trend compared to Placebo iTBS + APT. For each intervention we will also determine (2ii) presence of persisting effects of Active iTBS and Active iTBS + APT in the short-term, long-term and cumulatively. Using the PE measures specified in Table 1 and t-tests, we will compare each PE measure for Active iTBS with Placebo iTBS and for Active iTBS + APT with Placebo iTBS + APT. Significant results will be reported. For (2iii), we will use one-tailed t-tests to identify presence of practice effects for MDS and AMPS. We will compare MDS and AMPS average peak gains after Placebo iTBS with average peak gains after Active iTBS. If the average Placebo iTBS peak gain is greater than the average Active iTBS peak gain for either MDS or AMPS, then we will repeat analyses above (for 2i and 2ii) using ImE and PE measures after adjusting them for the detected practice effects.

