Since we seek to identify one ROI as the optimal iTBS GIMME target and as each pathway is comprised of two ROIs, we will select one of the two ROIs comprising the pathway selected as the most important to cognitive function. This ROI is the ROI with the highest total degree. The graph theory metric of total degree quantifies the sum of in-degree (number of connections coming into the ROI) and out degree (outbound connections). As both in and out degree reflect importance of the ROI to cognition, we will use total degree to select the optimal brain region. If the total degree between the brain regions is equal, we will base the decision on TMS accessibility, Gray Matter Density and/or structural integrity.

Regarding testing Aim 4, the results from above GIMME modeling and decision criteria will, ultimately, test hypothesis that, within our study population of persons **with** moderate cognitive impairment from TBI, there are sub-types/sub-groups of persons with common brain circuitry important to cognition.

Past GIMME work indicates that a minimum of 7 persons with moderate cognitive impairment from TBI will be sufficient to identify an optimal group-level model as well as sub-types/subgroups. That is, 7 participants per diagnosis, here moderate cognitive impairment from TBI, has consistently identified an optimal group-level model as well as subgroups within this diagnosis. Thus, we will strive to enroll at least 7 participants into these optional studies.

**AIM 5:** Determine immediate gains in working memory and performance of complex IADL after provision of a single session of iTBS targeting to the same location in the L DLPFC after a single session of iTBS targeting the optimal GIMME brain target. We hypothesize that average gains in working memory and functional performance after a single iTBS session site will be

significantly different according to site of stimulation (GIMME site). For each iTBS session, we will compute pre and post iTBS MDS and AMPS scores to be used to compute change in working memory and functional performance of IADL. For each outcome and each treatment site, the mean change will be computed. Using student t-tests, we will compare mean change in working memory and mean change in functional performance between the L DLPFC vs GIMME sites. This will allow us to examine the concept that treatment sites personalized by ROI structure is or is not important for optimizing clinical benefits of iTBS.

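### Aim 2iii sets out to measure practice gains under Placebo iTBS, but its Placebo-versus-Active contrast cancels shared practice, and the re-analysis trigger follows the treatment result

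*Combined protocol and SAP*

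**What the plan says.** Section 2.0 gives practice effects a place among the pilot's purposes: "The pilot data will inform the need to account for practice effects while estimating magnitude and duration of treatment effects". Section 3.0, Aim 2 (2iii), then defines the target as a quantity inside one arm: "presence and magnitude of practice effects by testing whether prior exposure to MDS or AMPS results in MDS or AMPS gains for Placebo iTBS".

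Section 5.6 analyses something else. It names one-tailed t-tests for detecting practice and continues: "We will compare MDS and AMPS average peak gains after Placebo iTBS with average peak gains after Active iTBS". The next sentence sets the condition for repeating 2i and 2ii with practice-adjusted measures: "If the average Placebo iTBS peak gain is greater than the average Active iTBS peak gain for either MDS or AMPS". It does not say whether a numerical excess is enough or significance is needed, nor how scores would be adjusted.

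Section 5.1 fixes the numbers available. Veterans in equal numbers from each diagnosis "within each iTBS group will be randomly assigned to be tested with the Modified Digit Span (MDS) or AMPS" for the first session, and they switch to the other test on Study-Day 3. Section 5.5 gives every participant the MDS forms in the same order.

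**The concern.** The objective asks how much Placebo Veterans gain from repeated testing. The analysis asks whether they gain more than Active Veterans, using the same two arms as the treatment test in 2i. Shared practice cannot appear in that difference. If practice differs by arm, the contrast shows only that difference, mixed with any treatment effect.

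Two things are at stake.

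- **The pilot estimate.** The Placebo mean peak gain is computed as an input, but it has no test, no confidence interval and no stated role as the estimate of practice.
- **Comparisons across sessions, where practice need not cancel.** Section 3.0 plans one: "we will compare Maximum Cognitive Gains (MCG) on MDS with MCG on AMPS between the Active iTBS and Active iTBS + APT groups". Active iTBS is given on Study-Day 2 and Active iTBS + APT on Study-Day 3. Aim 5 plans another: "we will compare mean change in working memory and mean change in functional performance between the L DLPFC vs GIMME sites". The GIMME site is stimulated on the optional Day 5, and the 2iii rule does not reach that comparison.

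The rule is also result-dependent: an adjustment with no stated method is run only when the result goes against Active.

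**Working it through.** **Inputs.** 24 Veterans per arm (sections 3.0 and 5.6), split evenly between MDS and AMPS on Study-Day 2 (section 5.1), gives 24/2 = 12 per arm per outcome. Effect sizes 0.35, 0.60 and 0.90 are those in section 5.6. Assumed: gain SD of 1; test level 0.05 (the plan gives only an FDR level of .05); independent MDS and AMPS triggers, because different Veterans supply them on that day.

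**The plan's own figure.** At an effect of 0.90, 80% power and two-sided 0.05, the t-based sample size is 20.4, so 21 per group, as stated. 42/(1 − 0.12) = 47.7, so 48. Nothing below depends on this beyond the effect-size scale.

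**Cancellation.** Let practice be pP in Placebo and pA in Active, and the treatment effect d.

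Placebo − Active = pP − (pA + d) = (pP − pA) − d

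If pP = pA, this is −d, whatever the size of practice.

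**Trigger read as a comparison of means.**

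P(one outcome) = Φ(−(d + pA − pP)/√(2/n)); P(either) = 1 − (1 − P)²

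For n = 12, √(2/12) = 0.408. At d = 0.90: Φ(−0.90/0.408) = Φ(−2.20) = 0.0137, and 1 − (1 − 0.0137)² = 0.027.

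| Treatment effect (equal practice) | One outcome | Either outcome |
|---|---|---|
| 0 | 50% | 75% |
| 0.35 SD | 19.6% | 35.3% |
| 0.60 SD | 7.1% | 13.7% |
| 0.90 SD | 1.4% | 2.7% |

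With 10 per arm, the either-outcome rate at 0.90 SD is 4.4%. In simulation (200,000 trials per setting) with shared practice of 0, 0.5, 1 or 2 SD, that rate at n = 12 stayed at 74.9 to 75.0% for d = 0 and 2.70 to 2.75% for d = 0.90.

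**Trigger read as one-tailed significance at 0.05 (df 22).** Either outcome: 1 − 0.95² = 9.75% with no effect, and 0.015% at 0.90 SD. Benjamini-Hochberg over the two tests lowers the first figure to about 5%.

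**Unequal practice, no treatment effect, Placebo practice 0.5 SD.** The either-outcome rate is 93% if Active practice is 0.25 SD and 47% if it is 0.75 SD. The quantity 2iii wants is the same in both cases.

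**AMPS exposures before each comparison.** The Study-Day 2 immediate test is preceded by screening and B0: two. A Study-Day 3 AMPS immediate test is preceded by screening and B0 to B2: four. Day 5 is preceded by screening, B0 to B4 and three immediate tests: nine. If within-session practice differed between Study-Days 2 and 3 by an assumed 0.25 or 0.5 SD, a 12 v 12 two-sided t-test with no APT effect would be significant in 9% or 22% of trials, before any FDR control.

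**What a direct estimate can deliver.** The 95% CI half-width for a within-Placebo mean change is t(0.975, n−1)/√n: 2.201/√12 = 0.64 SD, or 0.72 SD with 10 Veterans. The estimate should not use the peak. In simulation with no practice at all, the best of three scores minus a baseline (independent errors, SD 0.707) averaged a gain of 0.60, and a one-sided test against zero rejected 71% of the time at n = 12.

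**The case against.** - **The first 2iii sentence could mean a test of Placebo gain against zero**, with the Placebo-Active comparison serving only the adjustment rule. This is possible, but the comparison is the only contrast given. On that reading the wording is still unclear and the trigger is still wrong.
- **Practice information arises anyway.** The group-by-time mixed models under 2i contain a Placebo time trend, and gains are computed by intervention. That is true, and the data will exist. The plan assigns neither to 2iii nor to the trigger.
- **The randomised comparisons are safe.** This stands in full. Shared practice does not bias Active minus Placebo or Aim 1, and subtracting 0.5 from both arms left the t statistic unchanged. The plan also repeats the analyses and does not replace them.
- **The cross-session harm is limited.** Section 5.6 tests Aim 2 through concurrent Placebo contrasts; the Active iTBS versus Active iTBS + APT comparison appears in section 3.0. Each AMPS uses a new task, and no Veteran takes MDS on both Study-Day 2 and Study-Day 3. Aim 5 is exploratory. These points reduce the weight of the harm. But section 3.0 does state the comparison, Aim 5 does test across sessions, and a new task does not rule out familiarity with the procedure. The 0.25 and 0.5 SD practice differences are assumptions.
- **The significance-reading rate ignores FDR control.** This is fair: 9.75% becomes about 5% over the two tests. The rate still responds to treatment and not to practice.

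**Conclusion.** The concern holds. As written, 2iii cannot supply the presence and magnitude of practice that section 3.0 promises, and the rule for a practice-adjusted repeat is driven by the treatment difference. On the means reading it fires for either outcome in 75% of trials with no treatment effect, even with zero practice, and in 2.7% at the planning effect, however large shared practice is. Requiring significance changes the rates but not the dependence. The percentages rest on 12 per arm per outcome, gain SD 1, independent triggers and, except where stated, equal additive practice. The mismatch between objective and analysis rests on none of these.

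This should be fixed. The damage is confined to the practice estimate and to comparisons across sessions; the randomised treatment contrasts stand.

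**What to change.** 1. **Replace the 2iii contrast with a within-Placebo change**, with a 95% CI and a one-sample or paired test, at a named administration or the mean of the three, not the peak. Name one primary estimate per outcome from Study-Day 2, before any APT, in the roughly 12 Placebo Veterans assigned to that test. For AMPS, use B0 to the mean of the three post-iTBS tests. For MDS, use first to third administration, because the visit schedule lists MDS only after iTBS. State that MDS change cannot be separated from form difficulty under the fixed form order, and that any within-Placebo change includes placebo response and fatigue.
2. **As secondary, report Placebo B0–B1 and B0–B2 change in AMPS and WAIS-IV Digit Span separately by the randomised Study-Day 2 test.** Pooling would mix Veterans with three and with no intervening tests of that type. The subgroup difference is a randomised estimate of the effect of the extra exposures. For Digit Span it measures carry-over from MDS, free of MDS form difficulty, and not MDS practice itself. Testing load differs (Table 2: 1.5 h per AMPS, 0.2 h per MDS), so B0–B1 carries more fatigue than B0–B2. At 12 v 12 the half-width is 2.074 × √(2/12) = 0.85 SD, with two-sided power of 22%, 47% and 65% at 0.5, 0.8 and 1.0 SD. Label any change after Study-Day 3 treatment as including APT.
3. **Delete the trigger.** Keep unadjusted Active minus Placebo as the treatment estimate. Limit practice adjustment to a pre-specified sensitivity analysis of within-arm and cross-session comparisons, with its method stated, run whatever the direction of the result.

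The cost is SAP wording. All the data are already scheduled; the price is an imprecise practice estimate, which should be reported as such.

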## Abstract

The purpose of this SPiRE is to identify the supports and barriers to scalability of Veteran-tailored iTBS and APT across neurologic conditions, with the longer-term goal of providing an empirical basis for the tailoring of a broader range of cognitive rehabilitation strategies to optimize each Veteran's cognitive function in daily life. After Veterans receive standard cognitive rehabilitation, cognitive impairments often persist and if they do make gains there is limited carry-over to daily function. The tenets of precision neurorehabilitation suggest that tailored interventions will optimize gains and carry-over, but precision-tailoring of cognitive rehabilitation will only be possible if researchers develop and test scalable approaches for identifying, organizing, and analyzing the multitude of Veteran-specific variables driving and influencing treatment responsiveness. This project addresses long-standing scientific barriers to understanding treatment responsiveness, particularly study sample heterogeneity and individual variability. We address study sample heterogeneity by linking Veterans, across TBI and ischemic stroke, according to levels of cognitive impairment. We create a cohort of Veterans with a homogeneous level of cognitive impairment, thereby enabling explication of person-centric factors influencing treatment responsiveness and carry-over to daily function. Advancing understanding of the basic study design elements will be achieved by leveraging our knowledge of intermittent Theta Burst Stimulation (iTBS) and iTBS paired with Attention Processing Training exercises (iTBS + APT). iTBS is advantageous as it robustly improves working memory with just one treatment session. These interventions, together, are advantageous as they can each be tailored to a Veteran's unique cognitive challenges and to target the neural site, unique to each Veteran's neuropathology. These two interventions also directly address cognitive deficits, while simultaneously inducing neuroplasticity in neural regions hampered or impaired by neural injury. We will study Veterans with moderately impaired cognition who, after standard cognitive rehabilitation, continue to struggle with daily life requiring assistance with complex instrumental activities of daily living (IADL). Veterans will participate in a series of two within-subject treatment studies, conducted on two separate days, 2-weeks apart. Veterans will be randomly assigned to first receive a single session of Active iTBS or Placebo iTBS and then they will receive APT paired with their assigned iTBS (Active iTBS + APT vs Placebo iTBS + APT). We will test if diagnosis moderates the effects of these interventions on both immediate and persisting change in cognition. For immediate effects, we use a novel testing battery and for persisting gains we use established and feasible neuropsychological tests as well as an established test of cognitive function during IADL. Results will be used to obtain pilot data and examine feasibility in terms of study attrition relative to Veteran fatigue, mood, and Veteran reports of suitability of key aspects of the study design. These findings will be used to develop a future merit within-subject cross-over study examining the overarching hypothesis that tailored iTBS and APT applied to a transdiagnostic sample and subsequently matched to a Veteran, according to a biotype algorithm, will result in better functional performance of Veteran-valued IADL.

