#### *In-Person Eligibility Confirmation:*

Veterans who meet all inclusion/exclusion criteria throughout the phone screening process will be consented for participation and proceed to in-person eligibility confirmation. The final screening step involves in-person testing at Hines VA to confirm that cognitive impairments are moderately impaired in capacity and function as determined by a battery of clinician rated tests including RBANS, WAIS-V, DKEFS, BRIEF, Dot Counting Test and AMPS. We measure cognitive capacity according to neuropsychological tests that correlate with functional

disability. We developed a testing battery that can be used to determine study eligibility and that can be feasibly repeated to use as an outcome indicative of persisting cognitive gains (Table 2). The Audit C and DAST-10 will be completed at this time.

*Alcohol and Substance Use:* As part of eligibility screening, during the in-person screening, the participant will complete the following two self-report tests:

The AUDIT-C is a brief alcohol screening instrument that identifies persons who likely to be hazardous drinkers or have active AUD (including alcohol abuse or dependence). The AUDIT-C has 3 questions and is scored on a scale of 0-12. Each AUDIT-C question has 5 answer choices valued from 0 points to 4 points. In men, a score of 4 or more is considered positive, optimal for identifying hazardous drinking or active alcohol use disorders. In women, a score of 3 or more is considered positive. Generally, the higher the score, the more likely it is that a person's drinking is affecting his or her safety.

The DAST, a NIDA CTN common data element, is a brief, self-report instrument for population screening, clinical case finding and treatment evaluation research. The DAST-10 is a 10-item self-report instrument that has been condensed from the 28-item DAST. Scores range from 0 to 10 with scores of 1-2 being considered low level problems that should be monitored with re-assessments periodically whereas further evaluation is indicated with a score of 3 or more.

Persons with alcohol use disorder (AUD) and/or substance use disorder (SUD) diagnoses confirmed by clinical and/or scientific experts (e.g., Research Neuropsychiatrist [name], Neuropsychologist [name], Neurologist/Epileptologist [name]) and/or scientific subject matter expert (e.g., [name]) will be excluded.

[figure not shown]

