### Study-Day 0 (In Person Eligibility Screening) (2-3 hours)

1. Complete questionnaires and testing
  - a. Audit-C and DAST-10

- b. Testing questionnaires
- c. Demographic information collection

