**Study-Day 1 (~5 hours) (may occur over 2 days):**

- 1. Complete tests/questionnaires that are not repeated. Some are collected for use as covariates (Table 2) and some are needed for treatment preparation.
  - a. Baseline testing battery
  - b. APT Baseline
  - c. fMRI-to be completed at NU CTI
  - d. Motor Threshold
  - e. Baseline EEG\*
- 2. Rating suitability of the number and types of tests 1-3.

\*EEG to be completed prior and reviewed by physician prior to Motor Threshold

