For Aim 3, we will compute study attrition as percent of participants dropping out after Study-Day 2 and after Study-Day 3. We will examine whether or not these attrition rates differ (3i) by stroke and TBI groups using chi-square. To examine if Veteran's with stroke and TBI have (3ii) different perceptions regarding the suitability of the number and type of tests and number of study-days, we will compare each group's average ratings, by suitability index, using t-tests. To explore the relationship between perceived suitability and fatigue as well as mood (3iii), we will compute Pearson correlations at each of the 5-timepoints (B0 through B4) between average ratings of suitability indices 1 through 3 and averages for each of the two fatigue measures and each of the five mood measures [5x (3x2) + 5x (3x5) = 105 correlations]. We will also compute correlations for average suitability indices 7 through 8 collected on Study-Day 4 (B4) with the averages from that same day for each of the two fatigue measures and each of the five mood measures [1x (2x2) + 1x (2x5) = 14 correlations]. We will test the significance of each correlation using Fisher Z test and results will be interpreted accordingly.

Aims 2 and 3 involve multiple comparisons. Bonferroni correction of type I error rate is very conservative, and, at this early research stage, it could mask important findings. Thus, we will control for false discovery rate (FDR) using an FDR level of .05.

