## 5.7 Withdrawal of Subjects

Study participants will be informed during the consent process that their participation in the study protocol is voluntary, and they may choose to discontinue research participation at any time. Discontinuation of research participation will not impact medical care received outside of the research study. Individuals may choose to withdraw from the study for medical or non-medical reasons. If withdrawal from the study occurs during the provision of iTBS, regardless of whether this withdrawal is related or unrelated to the protocol, participants will be evaluated by the study physician and a medically appropriate plan for follow up will be established in a manner that maintains the safety of the research participant. The PI may also choose to withdraw a participant from the study if by the PI's judgment continuation in the study is not in the best interest of the participant for health or safety reasons, non-compliance with study procedures or loss of funding for the project.

Every attempt will be made to retain research participants in this study. Research participants who do not complete their study participation will be replaced only if they withdraw prior to any research procedures past the baseline measures. Unless a research participant revokes his/her consent to use their health information (i.e. revocation of HIPAA Authorization), any data collected prior to study withdrawal will be used in data analysis.

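### Aim 3 attrition omits eligible Veterans who leave before Study-Day 2 and are replaced, so the feasibility measure cannot reflect early burden-related loss

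*Combined protocol and SAP*

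**What the plan says.** Section 5.6 (Data Analysis, Aim 3) defines the measure: "we will compute study attrition as percent of participants dropping out after Study-Day 2 and after Study-Day 3". These rates are then compared between stroke and TBI by chi-square. No earlier time point is named and no denominator is stated.

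Section 5.7 (Withdrawal of Subjects) says that participants who do not complete the study "will be replaced only if they withdraw prior to any research procedures past the baseline measures". It adds that, unless authorization is revoked, "any data collected prior to study withdrawal will be used in data analysis".

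The Abstract gives attrition its role: results will be used to "examine feasibility in terms of study attrition relative to Veteran fatigue, mood, and Veteran reports of suitability". Section 3.0 states hypothesis 3i: "Attrition rates do not differ by stroke and TBI groups".

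On timing, section 5.1 (In-Person Eligibility Confirmation) says that Veterans who pass the telephone steps "will be consented for participation and proceed to in-person eligibility confirmation", so consent precedes Day 0. Day 0 is listed at 2 to 3 hours. The next visit is headed "Study-Day 1 (~5 hours) (may occur over 2 days") and holds the baseline battery, APT baseline, fMRI, motor threshold and EEG. Suitability items 1 to 3 are rated that day. Study-Days 2 and 3 are about 8 hours each.

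**The concern.** The attrition window opens only after Study-Day 2, while the replacement rule operates before it. A Veteran who passes eligibility, goes through Day 1 and then declines to return is replaced, and no stated rate records the departure. Any number of such Veterans could leave without changing the reported figure.

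This matters because Aim 3 asks whether the number and type of tests and the number of study-days suit these Veterans. The plan already treats Day 1 as part of that question, since it collects suitability ratings on that day. Leaving after Day 1 is direct evidence on suitability, and the attrition measure does not see it. A pilot meant to inform a later cross-over study could then report better retention than its recruits actually showed.

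There is also a gap at the boundary. The baseline measures in section 5.7 are not tied to a study day, and Study-Day 2 begins with a pre-treatment persisting-effects battery. A participant who stops partway through that day is not clearly eligible for replacement and has not clearly dropped out after Study-Day 2.

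**Working it through.** **Inputs from the documents.** Planned enrolment is 48, with 42 required and a 12% allowance (section 5.6). Visit lengths are 2 to 3 h for Day 0 and about 5 h for Day 1 (section 5.1). The attrition definition is in section 5.6 and the replacement rule in section 5.7.

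**Inputs assumed.** L is the number of dropouts after Study-Day 2 or Study-Day 3, with the two planned rates pooled for simplicity. e is the number of eligible Veterans who withdraw earlier and are replaced. The documents give neither. The denominator of the planned rate is taken as 48, because replacement restores that number.

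**Step 1, the plan's own figure.** 42/(1 − 0.12) = 47.7, rounded up to 48. This agrees with the plan. The implied number of later losses is 48 − 42 = 6, so L = 6 is a natural illustration.

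**Step 2, exposure before the window opens.** 2 to 3 h + about 5 h = about 7 to 8 h.

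**Step 3, the two rates.** Planned rate = L/48. All-starter rate = (L + e)/(48 + e).

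| L | e | Planned rate | All-starter rate | Difference (points) |
|---|---|---|---|---|
| 6 | 0 | 6/48 = 12.5% | 6/48 = 12.5% | 0 |
| 6 | 2 | 12.5% | 8/50 = 16.0% | 3.5 |
| 6 | 4 | 12.5% | 10/52 = 19.2% | 6.7 |
| 6 | 8 | 12.5% | 14/56 = 25.0% | 12.5 |
| 0 | 2 | 0% | 2/50 = 4.0% | 4.0 |
| 0 | 8 | 0% | 8/56 = 14.3% | 14.3 |

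The planned rate does not depend on e. If the unstated denominator were read to include replaced Veterans while the numerator still left them out, the figure would be lower still: with L = 6 and e = 4, 6/52 = 11.5%.

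**Step 4, the stroke/TBI comparison (3i).** Assume 3 later dropouts in each diagnosis (24 each) and, as an extreme, 6 early withdrawals all in one diagnosis. The plan compares 3/24 = 12.5% with 3/24 = 12.5%. The all-starter rates are 9/30 = 30.0% and 3/24 = 12.5%. Chi-square without continuity correction gives p = 0.12, and Fisher's exact test gives p = 0.19.

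**The case against.** The strongest reply is that replacing people lost before treatment is sound practice. It protects power, and for sizing a treatment comparison the relevant loss is that after treatment starts, which the plan measures following its two longest visits. This stands. The objection is not to replacement but to letting it remove losses from a feasibility endpoint.

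Five stronger readings are tempting, and the documents do not support them.

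- **That 19.2% or 25.0% breaches the plan's 12%.** The 12% inflates 42 analysable subjects to 48. A replaced Veteran costs no analysable subject, so the allowance is not the comparator.
- **That all loss between Day 0 and Study-Day 2 is burden.** The baseline EEG, urine pregnancy screen, C-SSRS and repeated MRI safety checklist all come at or after baseline and can exclude a participant. Counting those exclusions as dropout would overstate burden.
- **That early leavers are discarded entirely.** Section 5.7 keeps data collected before withdrawal, so Day 1 suitability ratings may still be analysed. What is missing is their departure from any attrition rate.
- **That loss during both 8-hour days goes uncounted.** Someone who leaves during Study-Day 3 has left after Study-Day 2. Only leaving during Study-Day 2 is ambiguous.
- **That the result sizes the next trial, or that a detectable stroke/TBI difference is being hidden.** The Abstract says only that findings will be used to develop a future study, and even the extreme split in Step 4 would not reach significance at 0.05.

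**Conclusion.** The point holds as a defect in how the feasibility measure is defined. On the stated rules, no attrition rate includes consented, eligible Veterans who leave after Day 0 or Day 1, and the status of someone who leaves during Study-Day 2 is unclear. The direction is certain: the reported rate is too low whenever such loss occurs and correct when none does. The size is not knowable from the documents. With 6 later dropouts and 2 to 8 early withdrawals, all assumed, the understatement runs from 3.5 to 12.5 percentage points. The effect on 3i is descriptive: rates by diagnosis could look equal when they are not, although a test at this sample size would probably not separate them. The analyses of Aims 1 and 2 and the sample size of 48 are unaffected.

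**What to change.** 1. In section 5.6, keep the two planned rates and report them as components.
2. Add attrition by stage: after Day 0, after Day 1, during Study-Day 2, after Study-Day 2 (including during Study-Day 3), and after Study-Day 3. Use as the base all consented Veterans who passed Day 0 eligibility, including those later replaced. State the denominator at each stage, and report by diagnosis and reason.
3. List exclusions after Day 0 for safety or eligibility (EEG, pregnancy screen, C-SSRS, MRI checklist) separately from voluntary withdrawals. Veterans who fail Day 0 eligibility are screen failures and stay out of attrition.
4. In section 5.7, tie the baseline measures to a study day, and say whether a participant who leaves during Study-Day 2 is replaced and at which stage that loss is counted.

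This needs no new visit or test, only slightly more tabulation of enrolment and withdrawal records already held. The stated attrition may look less favourable.
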